6.1.Primary objective: To evaluate the feasibility of the parallel experimental design, the willingness to participate of eligible patients, and the outcome measures for conducting a randomized phase III clinical experiment comparing partial myometrial resection with hysterectomy in patients with PAS, carried out in 3 different centers, including Fundación Valle del Lili, in a period of 24 months.

6.2.Specific objectives:

- 1. To measure the proportion of eligible patients who agree to participate in this comparison.
- 2. To measure the percentage of screening failure.
- 3. To describe the confirmation of the presence or absence of placental accretenotic spectrum in each case.
- 4. To identify the degree of variability between the different methods of measuring intraoperative bleeding in each of the techniques.

6.3.Secondary objectives:

- 1. Clinical and sociodemographic characterization of the patient.
- 2. To identify the characteristics of the patient's current pregnancy.
- 3. To describe the clinical outcomes of interest in patients randomized to hysterectomy or partial myometrial resection.
- 4. To categorize the severity of surgical complications according to the Clavien Dindo classification.

7. Hypothesis

7.1.Primary hypothesis: It is possible to recruit, randomize, operate and follow-up patients recruited for an experiment comparing two surgical techniques in PAS (Hysterectomy Vs Partial myometrial resection) in a period of 24 months or less.

8. Outcomes measures/endpoints:

8.1.Primary endpoints:

- Proportion of eligible patients who agree to participate in the study.
- Screening failure percentage
- Percentage of patients assigned to each arm of the study.
- Percentage of patients with crossover between assigned study arms.
- Number of subjects who complete follow-up at 42 days postpartum.

8.2. Secondary endpoints:

- Maternal death
- Intra-surgical bleeding volume measured in mL.
- Blood component transfusion requirement, median transfusion of red blood cell units (RBCU)
- Compliance with at least one WHO Near Miss criterion (See Appendix 1)
- Ureteral injuries.
- Bladder injuries
- Need for surgical reoperation.
- Admission to the Intensive Care Unit.
- Days of post-operative hospital stay.
- Use of uterine tamponade with hydrostatic balloons.
- Presence of supra fascial hematoma
- Presence of postoperative ileus
- Vital status of the newborn
- Weight of the newborn

9. Methods:

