Women with a previous cesarean section, anterior placenta previa, and imaging (ultrasound or MRI) with signs suggestive of PAS will be eligible to participate (See Appendix 2: Definition of a suspected PAS case). Informed consent will be requested from these patients prior to surgery. Considering that these are pregnant women, the participation of the husband or spouse will be included in the informed consent (Appendix 7). In the event that the patient does not have a husband or spouse, the "Declaration of mother head of the family" will be filled out (Appendix 8).

Randomization will be carried out before starting the surgical procedure, with the aim of reducing the possibility of selection bias by the surgical team since there is no blinding.

It is possible that some patients who are eligible before surgery and who have signed the informed consent, will cease to be eligible if macroscopic signs suggestive of PAS are not found at laparotomy (See Appendix 2: Definition of confirmed PAS case) (that is, if present a false positive result of the prenatal diagnostic images), which has been described in up to 22.6%¹¹ of the cases. These patients will be considered screening failures in the recruitment process and will be excluded from the statistical analysis.

9.5.1. Inclusion criteria:

- Pregnant women over 18 years of age.
- History of previous cesarean section and anterior placenta previa
- Patients with prenatal diagnosis by ultrasound or MRI of PAS (See Appendix
 2: Definition of a suspected case of PAS), regardless of the suspected degree of severity of the disease.
- Requirement for surgical management of placental accreta on a scheduled basis.
- Patients without active vaginal bleeding in the period immediately before surgery (Patients entering the operating room without active bleeding).

9.5.2. Exclusion Criteria:

- Women without previous living children.

9.6. Sample size:

As the aim of the study is not to compare the effectiveness between interventions, a formal power calculation was not performed. A sample size of 60 participants. According to the estimated recruitment rate for each center, the following distribution is proposed: 36 patients from Indonesia, 12 patients from Argentina and 12 patients from Colombia to address the feasibility objectives.

9.7. Recruitment strategy:

9.7.1. Participant selection:

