Women with a previous cesarean section, anterior placenta previa, signs of PAS on ultrasound or prenatal magnetic resonance imaging (See Appendix 2: Suspicious case of

PAS) and who meet the inclusion criteria will be considered as possible candidates to participate in the study. Patients will be identified by the medical group and evaluated for their eligibility at the time of hospital admission before surgery.

Once the treating medical personnel confirm the eligibility of the patient, she will be provided with complete information about the study and the physical informed consent, the patient will have at least 48 hours to evaluate it, discuss it and decide whether or not she wishes to participate.

Participants who voluntarily decide to take part in the study will not receive any payment or remuneration as a result of their participation.

Some anonymized data of the women who decline their participation in the study and that will be used in the CONSORT report will include:

Date of cesarean section. Ethnicity Number of living children Reason why the patient is not eligible, or if she is eligible because she declined to participate.

Before the start of the surgical procedure, the clinical coordinator of the study will be in charge of revealing the surgical intervention to which the patient has been randomized to reduce the probability of selection bias since blinding is not possible in this study.

Once the laparotomy has been performed, the surgeon will define whether or not there are macroscopic signs on the anterior face of the uterus that confirm the diagnosis of PAS (See Appendix 2, Confirmed case of PAS). The clinical diagnostic criteria reported by the International Federation of Gynecology and Obstetrics (FIGO) will be used¹⁷.

At that time, if the diagnosis of PAS is confirmed, the randomized intervention will continue. If the diagnosis of PAS is not confirmed, the patient will be considered a screening failure.

The entire process from the disclosure of the randomization, the confirmation or exclusion of PAS and the performance of the randomized intervention will be supervised by the study coordinator in each hospital.

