If the diagnosis of PAS is ruled out (If the clinical criteria for PAS proposed by FIGO [Appendix 2] are not present), the patient is excluded from the study and subsequent surgical management will be defined by the treating surgical group.

If the diagnosis of PAS is confirmed by observing the clinical criteria endorsed by FIGO (Appendix 2), the patient's participation in the study is confirmed and the surgical procedure defined by randomization is continued, that is, one of the two arms of the study:

Primary hysterectomy: An incision will be made above the level of the placenta, delivering the newborn. Uterotonics will be administered, and spontaneous delivery of the placenta will be awaited using gentle traction. The absence of spontaneous separation of the placenta will confirm the diagnosis of PAS, the patient will undergo hysterectomy. The complete removal of the uterus will be attempted, including the cervix, the duration of the intervention and intraoperative blood loss will be recorded, as well as the damage to organs neighboring the uterus. In this arm of the study, hysterectomy will be performed in 100% of patients.

Partial myometrial resection: The technique described by Palacios-Jaraquemada et al⁵. will be followed. Briefly, the uterus will be dissected to free it from the posterior wall of

the bladder to the cervix. The vesico-uterine vessels will be ligated and the parametrial space will be visualized. The hysterotomy will be performed in the upper segment, immediately above the area of invasion of the myometrium. The entire invaded myometrium and the entire placenta will be removed. The uterus will repair itself in one or two layers. Intrauterine balloon tamponade will be used if indicated.

Post-operative care will be routine care according to the indication of the treating medical team.

To consult the detailed description of the interventions (hysterectomy and partial resection) and the procedures for the evaluation of clinical outcomes, see the standardized operating plan (See Appendix 4)

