- Abnormal macroscopic findings on the surface of the uterine serosa, the placental tissue invades through the surface of the uterus.

- It does not invade any organs, including the posterior bladder wall (there is a clear surgical plane between the uterus and the bladder)

Placenta percreta grade 3B: With invasion of the bladder wall:

- There are placental vessels that invade the bladder surface but not other organs.

- A clear plane between the bladder and the uterus cannot be identified

Placenta percreta grade 3C: With invasion of other pelvic organs:

- Placental vessels invade the round ligament, vaginal wall, lateral pelvic walls, or other pelvic organ (with or without invasion of the bladder)

APPENDIX 3

Inclusion and exclusion format Institution: ______ Clinic history: _____ Screening number:

Inclusion and exclusion criteria

	Inclusion criteria	Yes	No
1	Pregnant woman over 18 years of age		
2	History of previous cesarean section and previous placenta		
	previa		
3	Prenatal ultrasound or magnetic resonance diagnosis of PAS.		
	(Appendix 2, Suspected case of PAS) regardless of the		
	suspected degree of severity of the disease.		
4	Requirement for surgical management of placental accreta on a		
	scheduled basis.		
5	Patients without active vaginal bleeding in the period		
	immediately prior to surgery (Patients entering the operating		
	room without active bleeding).		

	Exclusion criteria	Si	No
1	Woman without children or newborns		

Flogible patient	Si	No
Elegiole patient		

Appendix 4

Screening summary Institution:

		7					
	Identification					oation	Not
	Date	Age	Name	ID	If	If	participating
					Patient	Patient	causes
					is	is not	(number
					elegible	elegible	according to
					Asigned	Asigned	list)
					numer	numer	
					(Group	(Group	
					186)	189)	
1							
2							
3							
4							
5							
6							
7							
8							

Not partipating causes				
1 Some exclusion criteria				
2	Denial of consent			

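### Does dropping women whose PAS is ruled out at laparotomy bias the consent proportion (primary endpoint 1)?

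*Combined protocol and SAP*

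**What the plan says.** Section 8.1 lists, as the first primary endpoint, "Proportion of eligible patients who agree to participate in the study". This serves the part of the primary objective (6.1) that concerns "the willingness to participate of eligible patients". Neither place states a time point or a denominator.

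Section 9.4 first makes women eligible on obstetric history and prenatal imaging, with consent sought before surgery. It then turns to women "who have signed the informed consent, will cease to be eligible if macroscopic signs suggestive of PAS are not found at laparotomy", and continues: "These patients will be considered screening failures in the recruitment process and will be excluded from the statistical analysis". Section 9.11 repeats that, if PAS is ruled out, "the patient is excluded from the study and subsequent surgical management will be defined by the treating surgical group".

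Section 9.7.1 gives the order of events: eligibility is confirmed, the woman is informed, she has at least 48 hours to decide, and the allocation is revealed just before surgery. The data kept on non-participants are "Date of cesarean section. Ethnicity Number of living children Reason why the patient is not eligible", or the reason for declining.

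Section 15 counts the women who agreed. It defines a screening failure as a woman who agreed and whose PAS was then ruled out during surgery. The Appendix 4 log has two causes of non-participation: an exclusion criterion, and "Denial of consent". Section 9.6 gives "A sample size of 60 participants", split 36, 12 and 12 by country.

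**The concern.** Section 9.4 uses the word eligible in two senses: on imaging before surgery, and after the uterus has been inspected. Only women who agreed to take part can pass from the first sense to the second, because no intraoperative finding is listed for decliners. A rule that removes false positives from one side of a proportion and leaves them on the other distorts it.

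The consequence would reach the next trial, since section 3 says this study is meant to allow its planning. Screening failure is a separate primary endpoint. A planner who took an understated consent proportion and multiplied it by one minus the screening-failure proportion would discount the false positives twice, and would overstate the number of women to approach.

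**Working it through.** **Inputs.** The false-positive share f is up to 22.6% (9.4) and up to a quarter (section 1, Introduction). Both are upper figures. The true consent proportion p is not in the documents, so 50% to 90% is assumed. It is also assumed that f is the same in consenters and decliners and that every consenter is operated on. The plan states no consent figure to reproduce; its only related arithmetic is 36 + 12 + 12 = 60, which holds.

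**Reading A: counted at the consent decision.** Everyone who agreed, over everyone eligible before surgery, gives p. The bias is 0.

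**Reading B: 9.4 applied to consenters only.** The reported proportion is p(1 − f)/(1 − pf), and the understatement is pf(1 − p)/(1 − pf).

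| p (assumed) | Reported, f = 22.6% | Shortfall (points) | Reported, f = 25% | Shortfall (points) |
|---|---|---|---|---|
| 50% | 43.6% | 6.4 | 42.9% | 7.1 |
| 70% | 64.4% | 5.6 | 63.6% | 6.4 |
| 90% | 87.4% | 2.6 | 87.1% | 2.9 |

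Over all p, the largest shortfall is 6.4 points at f = 22.6% (p about 53%) and 7.2 at f = 25% (p about 54%). It is 4.1 at f = 15%, 2.6 at f = 10% and 1.3 at f = 5%. At f = 22.6% it is below 3 points once consent exceeds about 88%.

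**Counts at p = 70%, f = 22.6%.** With 60 confirmed women, 60/0.774 = 77.5 agreed, 77.5/0.7 = 110.7 were eligible and 33.2 declined; 60/(60 + 33.2) = 64.4%. If the 60 are randomised women instead, 46.4 are confirmed and 25.7 declined; 46.4/(46.4 + 25.7) = 64.4%. The unit of the 60 therefore does not enter the bias. The standard error at 70% is √(0.7 × 0.3/110.7) = 4.4 points.

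**Reading C: all who agreed, over the reduced eligible set.** This gives p/(1 − pf) = 0.7/0.8418 = 83.2%. It passes 100% once p exceeds 1/(1 + f), which is 82% at f = 22.6% and 80% at f = 25%.

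**Planning effect under B.** The number to approach is overstated by f(1 − p)/(1 − f): 0.226 × 0.3/0.774 = 8.8% at p = 70%. It runs from 2.9% (p = 90%, f = 22.6%) to 16.7% (p = 50%, f = 25%).

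**Which reading the text supports.**

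- Section 9.4 describes the women concerned as eligible before surgery, and 9.7.1 places confirmed eligibility ahead of the consent decision. Endpoint 1 is complete at that decision, before any laparotomy.
- Section 15 makes screening failures a subset of the women who agreed, so they belong in the numerator. A numerator fixed at consent calls for a denominator fixed at the same moment; Reading C mixes two moments.
- If the exclusion covered the feasibility endpoints, the women who make up endpoint 2 would be gone and endpoint 2 could not be reported. The scope that makes sense is the clinical summaries, which matches the confirmed-PAS study groups in 9.3.

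All three points lead to Reading A.

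**The case for a change.** The strongest case for a change is that 9.4 does not limit its exclusion to the clinical outcomes, while 9.14 covers feasibility and clinical results in one plan. Section 15 gives a numerator but no denominator. The same women could therefore yield 64.4%, 70% or 83.2%, a spread of about 19 points on a primary endpoint, and three centres fill in the log. Clarifying the text would cost almost nothing.

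It stands that the wording is loose, that the denominator is nowhere written down, and that the conditional arithmetic is right. It does not stand that the plan produces the bias: Readings B and C each need a choice that works against 9.7.1 or section 15, and B also defeats endpoint 2.

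Inconsistent logging is a small risk. Section 15 has a yes/no screening-failure variable for each patient, and the Appendix 11 surgical note repeats it, so these women can be identified however Appendix 4 is completed; a further code there would duplicate those fields. Section 9.13 gives the analysis to one independent statistician. Double discounting would also require a planner to ignore the separate counts of refusals and screening failures, although 9.7.1 foresees a CONSORT report. No progression threshold is attached to endpoint 1.

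The one-sided filter is also less absolute than it looks. Decliners belong to a population due for PAS surgery at these hospitals (9.2), and 10.1 says PAS variables are routinely collected there. Their laparotomy finding is unlisted, not necessarily unobtainable. Reading A does not need it.

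**Conclusion.** The concern does not call for a change. Taken together, sections 9.4, 9.7.1 and 15 fix endpoint 1 at the pre-surgical consent decision, where this bias is zero. What remains is an unstated denominator that a competent analyst would fill correctly.

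Only if the 9.4 exclusion were carried into endpoint 1 for consenters alone would the proportion be understated: by 0 to 6.4 points for a false-positive share up to 22.6%, and by up to 7.2 at 25%. Those figures rest on a consent rate that the documents do not give, on equal false-positive shares in consenters and decliners, and on treating ceilings as expected values. The unit of the 60 is a separate matter and does not alter them.

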Statistical analysis	It will be performed according to the principles of intention-to-treat analysis. Descriptive statistics will be used to summarize the feasibility results. According to the CONSORT guidelines for feasibility experiments, efficacy tests are not recommended, because the study is not designed to detect differences between types of surgery, therefore, for clinical outcomes the analyses will focus mainly on descriptive analyses using mean (standard deviation) or median (interquartile range) for continuous outcomes and absolute frequencies and percentages for categorical outcomes. For the specific objective of the degree of variability of the bleeding methods, the coefficient of variation of each method within the surgical techniques will be calculated. The STATA software version 14.0 ® will be used.					
Key Words	Placenta accreta spectrum, Hysterectomy, resective reconstructive treatment.					

Amendment	1.0			
Rationale				
Table of Contents	Included			
Synopsis	Included			
6.3 Specific objectives	Objective 1 is deleted: To evaluate the willingness of the team of gynecologists to recruit patients for a clinical experiment. This is eliminated because it would be 100% because the team of intensivist gynecologists of the placental accreta spectrum clinic have signed the log of responsibilities. Compliance with this agreement is difficult to measure because women who might be eligible are not known and were not identified by gynecologists. Objective 4 is deleted: To measure the frequency and describe the cross-over ratios in each group using random assignment of the intervention. This is eliminated because there is only one cross-over ratio. This ratio is described in section 9.4 Study groups of the protocol. Objective 5 is modified: The purpose of this objective is clarified, which is to measure how concordant the methods for measuring bleeding are. The secondary clinical outcomes or complications are by clinical diagnosis and there is no doubt about them. Objective 6 is deleted: To identify the administrative barriers to the performance of the randomly assigned procedure is eliminated because in this study there are no administrative withdrawals. Objective 7 is deleted: To evaluate the comparability and generalizability of the sample of patients studied is eliminated because in this type of study the patients are highly selected, with very strict criteria. Therefore, the comparability and generalizability is very low.			

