9.14. Statistical analysis plan

Statistical analysis will be performed in accordance with the principles of intention-totreat analysis. Descriptive statistics will be used to summarize the feasibility results. According to the CONSORT guide for feasibility experiments (Eldridge et al., 016), efficacy tests are not recommended, because the study is not designed to detect differences between the types of surgery, therefore, for the clinical outcomes analyzes will focus primarily on descriptive analyzes using the mean (standard deviation) or median (interquartile range) for continuous outcomes and absolute frequencies and percentages for categorical outcomes. For the specific objective of the degree of variability of the bleeding methods, the coefficient of variation of each method within the surgical techniques will be calculated. STATA version 14.0 ® software will be used.

9.15. Interim analysis:

An interim analysis will be carried out when 10 patients have been randomized, to evaluate possible factors to improve in the execution of the study. This interim analysis will be carried out by the executing institution and the research group.

10. Data collection, patient follow-up, study monitoring and clinical outcomes:

10.1. Data collection:

A CRF ("case report form") will be designed together with the systems support staff of Fundación Valle del Lili, the clinical history will be used as the source document, from which the data of interest will be obtained to be entered into the *RED Cap*® electronic platform where the variables to be studied will be recorded and the demographic data of the participants, obstetric history (pregnancy and parity) of previous surgeries that include cesarean deliveries or uterine curettage or other gynecological surgery will be collected, gestational age at diagnosis, gestational age at delivery, and birth outcome. Prenatal complications, particularly bleeding before delivery (number of episodes and quantity, blood transfusions) will be recorded.

The type of surgical procedure, the type of anesthesia, the duration of the procedure, the

surgical details, the volume of total intra-surgical bleeding, the details of the transfusion of blood components and the surgical complications, transfer to the Intensive Care Unit (ICU), length of stay in ICU in days / hours, the WHO Near Miss criteria (Appendix 1). Postoperative complications and the total length of hospital stay will be recorded.

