APPENDIX 5. STANDARDIZED OPERATIONAL PLAN

All study participants will have specific roles listed below.

Principal investigators at each center:

- [name]. Fundación Valle del Lili (Cali, Colombia)

- [name]. [name] General Hospital, Universitas Airlangga, (Surabaya, Indonesia)

- [name]. CEMIC University Hospital (Buenos Aires, Argentina)

Roles of the Principal Investigators:

- 1. Design of the study protocol, construction of documents necessary to meet the requirements of regulatory committees at Fundación Valle de Lili and other participating hospitals.
- 2. Identify candidate patients to participate in the study. Assess your eligibility using inclusion and exclusion criteria.
- 3. Notify all study participants of the identification of a potentially eligible study subject. A virtual chat will be used on the Microsoft Teams® platform where all the participants will find out when each of the three participating centers identifies a potential subject to be included.
- 4. Provide the patient with sufficient and clear information so that she can evaluate her potential participation in the study.
- 5. Obtain informed surgical and study consent including hysterectomy and partial myometrial resection options.
- 6. Provide the study coordinator with the informed consents collected to be stored as part of the confidential study documentation.

When the first subject of the study is admitted, the principal investigator will provide the study coordinator with the informed consent completed within the first 24 hours after collection, in order to report it to the research ethics committee. For the other participants included, the principal investigator will have up to 1 week to provide consent to the coordinator for them to be reported to the ethics committee within the first 5 days of each month

- 7. Convene the study coordinator before starting the surgical intervention to reveal the result of the randomization and assign one of the two possible surgical procedures. The intervention will depend on the randomization according to the sequence that resides in the Red Cap® software
- 8. Confirm or rule out the diagnosis of PAS by observing clinical criteria during laparotomy:

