6. Verify that the procedure for obtaining informed consent from the research subject is done correctly by the principal investigator.

7. Safeguard the informed consents filled out as part of the confidential documentation of the study, if required.

8. Report to the ethics committee in biomedical research the inclusion of the first participant in the study within the first 24 hours of their inclusion with their respective informed consent.

9. Report to the ethics committee in biomedical research within the first 5 days of each month, the duly filled informed consents.

10. Be attentive to the call from the principal investigator advising the start of surgery to reveal to the surgical team the randomized intervention assigned to the patient. This procedure will be performed in person when possible, if the presence in the surgery room of the study coordinator or the quality monitor is not possible, a video call will be used in which the result of the test will be transmitted to the surgical group. randomization, before starting surgery

11. Support the principal investigator in the prospective collection of study variables within surgery, also support the subsequent registration of it in real time (within 24 hours) in the CRF of the Red Cap® virtual platform within maximum 7 days after surgery.

12. Support the principal investigator in the echography photos of prenatal diagnosis of PAS and the histology specimens photos collection.

13. Receive and respond to observations made by the data quality monitor of the other participating institutions.

14. Monitor the follow-up process of each of the randomized subjects in the event of any adverse event or serious adverse event to make their respective report to the ethics committee in biomedical research. (serious adverse events within the first 24 hours of occurrence and adverse events monthly)

15. In the event of serious adverse events, coordinate the meetings of the adverse event evaluation committee with the principal investigator.

16. In the event of any modification to the protocol or to the documentation corresponding to the study (Appendixes, informed consent or declaration of the mother of the head of the family), submit these changes in the form of an amendment to the ethics committee in biomedical research.

17. Support the main researcher in the writing and submission of the article resulting from the study.

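### The analysis is called intention-to-treat, but women randomised and then judged at laparotomy not to have PAS, by a surgeon who knows the arm, are removed from it

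*Combined protocol and SAP*

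**What the plan says.** On the analysis principle, 9.14 reads "Statistical analysis will be performed in accordance with the principles of intention-totreat analysis" and the synopsis reads "It will be performed according to the principles of intention-to-treat analysis". Neither mentions an exclusion or defines an analysis set.

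On who is analysed, 9.4 says of women without macroscopic signs of PAS at laparotomy: "These patients will be considered screening failures in the recruitment process and will be excluded from the statistical analysis". Section 9.11 and Appendix 5 (principal investigator role 8c) add that these women leave the study and that the treating surgeons decide their further management.

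On timing, 9.4 and 9.7.1 place randomisation and disclosure of the arm before surgery. Under Appendix 5, the investigator must "Convene the study coordinator before starting the surgical intervention to reveal the result of the randomization" (role 7) and the coordinator must "reveal to the surgical team the randomized intervention assigned to the patient" (coordinator function 10). Under 9.7.1, the surgeon then judges whether PAS is present.

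On what is to be described, secondary objective 3 in 6.3 is "To describe the clinical outcomes of interest in patients randomized to hysterectomy or partial myometrial resection", and specific objective 3 in 6.2 is "To describe the confirmation of the presence or absence of placental accretenotic spectrum in each case". The primary endpoints in 8.1 include the screening failure percentage, crossover and "Number of subjects who complete follow-up at 42 days postpartum".

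**The concern.** Under intention-to-treat, every randomised woman is analysed in her assigned arm. Following 9.4 instead gives a set chosen after randomisation by someone who knows the arm. Leaving out women who never had the condition can be defended if the judgement is made without knowledge of the arm, but here it is not.

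Two feasibility results are directly affected:

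- **42-day completion.** This is a primary endpoint, yet ruled-out women have left the study, so the number cannot describe everyone randomised.
- **Receipt of the assigned operation.** A ruled-out woman may receive neither study operation. That is not crossover, and nothing planned would show how often it happens among randomised women.

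The clinical data by arm matter too. Section 3 says they are to help plan the definitive trial, and section 2 proposes intra-surgical bleeding as that trial's primary outcome. Those data would come from confirmed women only, under a label that says otherwise.

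**Working it through.** **Step 1: the plan's own figure.** Section 9.6 gives 36 + 12 + 12 = 60, which adds up. No power calculation lies behind it, so there is nothing further to reproduce.

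**Step 2: order of events.**

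1. Consent, then randomisation before surgery (9.4).
2. The arm is revealed to the surgical team before surgery (9.7.1, 9.12, Appendix 5).
3. Laparotomy, at which the surgeon confirms or rules out PAS (9.7.1, 9.11, Appendix 5 role 8).
4. If PAS is ruled out, the woman leaves the study (9.11, role 8c) and the analysis (9.4).
5. If PAS is confirmed, the assigned operation proceeds (9.11).

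Exclusion at step 4 follows disclosure at step 2, so the analysed set is not the randomised set.

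**Step 3: passages that assume randomised women stay in.** Secondary objective 3 describes randomised patients. Section 10.5 ends the study 42 days after the last randomised patient's caesarean. Section 12.1 requires adverse events to be reported for 42 days from randomisation. Appendix 5 (coordinator function 14) has the coordinator follow each randomised subject for adverse events. All of these conflict with removing women at laparotomy.

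**Step 4: size.** Let p be the share ruled out. Section 9.4 gives up to 22.6%. The quarter in the Introduction cites the same reference as the 22.6% in section 2 and is probably a rounding, so it is not used as a separate bound. The 5% and 10% rows are assumptions that show the lower range.

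- If 60 are randomised: excluded = 60p, remaining = 60(1 − p), ceiling for 42-day completion among randomised women = 1 − p.
- If 60 are confirmed: randomised = 60/(1 − p), rounded up; ceiling = 60/randomised.

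| p | Excluded of 60 | Remaining | Ceiling | Randomised for 60 confirmed | Ruled out | Ceiling |
|---|---|---|---|---|---|---|
| 5% (assumed) | 3.0 | 57.0 | 95.0% | 64 | 4 | 93.8% |
| 10% (assumed) | 6.0 | 54.0 | 90.0% | 67 | 7 | 89.6% |
| 22.6% (9.4, upper) | 13.6 | 46.4 | 77.4% | 78 | 18 | 76.9% |

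For the last row, 60 × 0.226 = 13.56 and 60/0.774 = 77.5. At that rate, chance alone would put the number excluded of 60 between 8 and 20 (95% binomial range). By centre, 36/12/12 would become about 28/9/9.

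**Step 5: which 60?** Section 9.3 describes both groups as confirmed cases, 10.5 speaks of randomised patients, and the table shells in section 16 are headed n=60. The flowcharts in 9.8 and 9.9 are not available here. The available text does not settle it.

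**Step 6: what the planned data can show.** Section 15 records the randomisation arm and a yes/no screening failure for each woman, so rule-outs by arm can be derived. The operation performed has only two codes, so receipt of neither cannot be recorded. FIGO class has no code for absence of PAS. Histological confirmation already has a NO code. No table shell has a row for rule-outs.

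**The case against.** **The exclusion is disclosed and counted.** It appears in 9.4, 9.7.1, 9.11 and Appendix 5, and the screening failure percentage is a primary endpoint. The study is descriptive and plans no comparison between arms, so no error rate or power changes. This stands, and it limits the severity. It does not make the label right.

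**The ceiling on completion is only one minus the rule-out rate, and the endpoint is worded as a number.** True, but section 15 also asks for a percentage and gives no denominator. Anyone planning the definitive trial needs the figure for all randomised women.

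**Safeguards exist.** The coordinator supervises, findings are photographed and filmed, histology is collected, and the consent section mentions review by blind experts. None of these is given a say in who is analysed.

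**Much of the data is already planned.** This is correct for rule-outs by arm, and the standard surgical note (Appendix 11) records screening failure alongside bleeding and injuries. It would be wrong to infer that these women disappear from the record. What is not secured is their follow-up to day 42 and their place in the analysis.

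**A reader might infer that the exclusion test itself differs by arm.** The hysterectomy text in 9.11 and Appendix 5 treats failure of the placenta to separate as confirming PAS, and the resection text has no such step. The documents do not support that inference. Section 9.11 settles participation before the arm-specific steps, role 8a sets the check before hysterotomy in both arms, the hysterectomy arm is to receive hysterectomy without exception, and Appendix 10 records spontaneous delivery before the arms divide. A wording tension remains because some Appendix 2 criteria can be seen only once delivery of the placenta is attempted. It needs reconciling, but it is not evidence of an arm-dependent exclusion.

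**Conclusion.** The point holds and should be fixed. It is wrong as written, not merely short of detail, because 9.14 and the synopsis name one analysis and 9.4 prescribes another.

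At the protocol's upper rate of 22.6%, about 14 of 60 randomised women would be dropped, about 46 would be analysed, and 42-day completion could describe at most about 77% of those randomised. If 60 means confirmed women, about 78 would be randomised and about 18 ruled out. These are upper-end expectations, because 9.4 says up to 22.6%; at an assumed 5% the loss is 3 of 60.

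A reader might go further and conclude that bleeding by arm will be biased by some stated amount. The documents give neither a rule-out rate by arm nor bleeding in ruled-out women, so the size of any such bias cannot be worked out. What can be said is that the surgeon's knowledge of the arm leaves room for selection and that the current tables would not display it.

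**What to change.** 1. **9.14 and synopsis:** define an intention-to-treat set (all randomised women, by assigned arm) and a PAS-confirmed set labelled modified intention-to-treat. State which set each table uses.
2. **9.4, 9.7.1, 9.11 and Appendix 5 role 8c:** keep ruled-out women counted as screening failures, but retain them in data collection to day 42 and in the intention-to-treat set under their assigned arm. Their surgical management is not altered. Check that the consent form covers this follow-up.
3. **Sections 15 and 16:** add a code for neither operation to the surgical intervention performed and a code for no PAS to FIGO class. Report rule-outs and operation performed by assigned arm and centre. Show receipt of neither operation separately from crossover.
4. **9.6 and the n=60 shells:** state whether 60 counts randomised or confirmed women.
5. **9.11, Appendix 2, Appendix 5 and Appendix 10:** reconcile the passages on when and how PAS is confirmed. Which rule applies is for the investigators to decide.

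The cost is wording, one further analysis set, a table row and two codes, plus an ethics amendment (11.1) with the consent check. Day-42 follow-up would be added for up to about 14 women if 60 are randomised, or about 18 if 78 are. Labelling and rule-outs by arm could be repaired later from planned variables, but day-42 data not collected at the time may be lost, so item 2 is the most urgent.
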